1 INTRODUCTION

This statistical analysis plan (SAP) provides a technical and detailed elaboration of the statistical analyses of efficacy and safety data based on the study protocol Amendment 3.0 dated 21 December 2022. Specifications for tables, figures, and listings will be provided in a separate document.

For Italy, a country-specific protocol amendment (Amendment 3-IT finalized 12 July 2023) added an exclusion criterion is to exclude subjects with a hypersensitivity to pimavanserin, any of its metabolites, or any compounds listed as being present in this medication and the details of the Schwartz equation to exclude patients whose estimated glomerular filtration rate (eGFR) is <30 mL/min as calculated by the bedside Schwartz equation at the last visit of the antecedent study ACP-103-069.

2 OBJECTIVES

2.1 Primary Objective

To evaluate the long-term safety and tolerability of pimavanserin after 52 weeks of treatment in children and adolescents with autism spectrum disorder (ASD).

2.2 Secondary Objective

To evaluate the continued response to long-term pimavanserin treatment in children and adolescents with ASD.

2.3 Exploratory Objectives

To evaluate the continued benefit of long-term pimavanserin treatment on the symptoms of ASD, in children and adolescents with ASD in the following clinical areas:

- Aberrant Behavior Checklist (ABC) symptoms domains
- Maintenance of benefit
- Response to treatment

3 STUDY DESIGN

3.1 General Study Design

This study will be conducted as a 52-week, open-label extension study of the antecedent double-blind study (ACP-103-069) to determine the long-term safety and tolerability of pimavanserin for the treatment of irritability associated with ASD in children and adolescents (5 through 17

years old at the time of enrolling into the antecedent double-blind study). Approximately 60 global sites and approximately eight countries will participate in this study.

The study will have two periods:

- Open-label treatment period (52 weeks)
- Safety follow-up period (at least 30 days)

[figure not shown]
Subjects who have completed the antecedent double-blind study and who have shown no significant worsening of symptoms at the end of the study as evidenced by the CGI-I of irritability will be included in this long-term extension study.

All subjects will receive the “low dose” for their age group (10 mg/day for 5 through 12 years old, and 20 mg/day for 13 through 17 years old) for the first two weeks of the study. At the Week 2 visit, the dose may be increased to the “high dose” (20 mg/day for 5 through 12 years old, and 34 mg/day for 13 through 17 years old) based on the Investigator’s assessment of clinical response. After the Week 2 visit and up to and including the Week 20 visit, dose adjustments, either increases or decreases, may be made at any clinic visit (scheduled or unscheduled), based on the Investigator’s assessment of clinical response and tolerability.

During the treatment period, clinic visits will be conducted at Baseline, and Weeks 2, 6, 12, 20, 28, 36, 44, and 52, or upon early termination (ET) from the study. In addition to the visit performed at time of study completion or premature discontinuation, a follow-up safety assessment will be conducted by telephone call at approximately 4 weeks after the last dose of study drug.

The study design schematic is provided in [Figure 1](#).

Figure 1 Schematic of Study Design

Abbreviations: EOT=end of treatment; ET=early termination; yrs=years

^a A dose increase, based on the Investigator's assessment of clinical response, may be made at the Week 2 visit. After the Week 2 visit and up to and including the Week 20 visit, dose adjustments, either increases or decreases, may be made at any clinic visit (scheduled or unscheduled), based on the Investigator's assessment of clinical response and tolerability. No further dose adjustments are allowed after the Week 20 visit.

3.2 Schedule of Assessments

The schedule of events and assessments for the study is presented in [Appendix 21.1](#).

3.3 Randomization

Not applicable.

3.4 Blinding

Not applicable.

3.5 Determination of Sample Size

The planned sample size for this study is not based on statistical power but will depend on the number of subjects who complete the antecedent double-blind study, and who rollover into this open-label extension study.

Assuming a drop-out rate of 15% in the antecedent study, it is estimated that approximately 193 subjects will be eligible to enroll in this OLE. Assuming all 193 subjects do enroll, then according to the Rule of Three, the 95% confidence interval for the occurrence rate of an unobserved adverse event is estimated as (0, 1.6%).

3.6 Coronavirus Disease 2019

In the context of the global COVID-19 pandemic or other natural disaster, the mechanisms to record information on the potential impact of the COVID-19 pandemic on data itself, as well as data collection and integrity, will be implemented. The impact of COVID-19 on the statistical analysis is discussed in each of the relevant sections of this SAP.

4 ANALYSIS SETS

Safety Analysis Set

The Safety Analysis Set will include all subjects who received at least one dose of open-label study drug. The Safety Analysis Set will be used for all analyses.

5 GENERAL CONSIDERATIONS FOR DATA ANALYSES

5.1 Data Presentation Conventions

For continuous variables, the following summary statistics will be provided: number of subjects, mean, standard error of the mean (SE), standard deviation (SD), minimum, maximum, and median. Unless specified otherwise, means, medians, and confidence intervals (CIs) will be presented to one more decimal place than the raw data, and the SDs and SEs will be presented to

2 more decimal places than the raw data. Unless otherwise specified, the maximum number of decimal places is 4 and values will be truncated to 4 decimal places in situations where there are more than 4 decimal places. Wherever possible data will be decimal aligned.

For categorical variables, summaries will include the number and percentage of subjects in each category. For demographic and baseline characteristics, the number of subjects and the percentage of subjects with missing data will be summarized (if applicable), and the denominator for percentages will be the total number of subjects in the given cohort. Categories with zero counts will not have zero percentages displayed. Percentages will be presented to 1 decimal place.

No hypothesis testing is planned. Descriptive summaries of all safety and efficacy endpoints will be provided.

Values that are collected with “<” or “>” signs will generally be analysed as the numerical value without the sign in tables and figures. In listings, these data will be reported as collected with the sign.

Duration in years is calculated as number of days/365.25 and will be rounded to 1 digit after the decimal point (tenths) for presentation purposes.

Duration in months is calculated as (number of days/365.25)×12 and will be rounded to 1 digit after the decimal point (tenths) for presentation purposes.

All data captured in the Electronic Data Capture (EDC) system will be presented in the listings, unless otherwise specified.

5.1.1 Change from Baseline Summaries

Change from Baseline results for each continuous measure in the safety and efficacy analyses will be presented in two ways:

1. Main analysis: using the Baseline from ACP-103-070 (study -070) and reporting the changes across study -070 timepoints
2. Exploratory analysis: using the Baseline from the antecedent study (ACP-103-069) and reporting the changes across the timepoints of both the antecedent study and the open-label study -070.

5.2 Derived Variables

Assessment scale total scores and subscores may be derived within the analysis datasets. In the event that total scores and/or subscores are collected on the eCRF as well as derived, the derived values will be used for all analyses. Both the raw and derived scores will be presented in the listings.

5.2.1 Aberrant Behavior Checklist

The Aberrant Behavior Checklist (ABC) is a parent/caregiver-rated scale comprised of five empirically-derived subscales encompassing 58 items that describe various behavior problems ([Aman et al. 1985](#); [Kaat et al. 2014](#)). The subscales have been labeled as follows:

- I. Irritability (irritability, agitation, and crying): Items 2, 4, 8, 10, 14, 19, 25, 29, 34, 36, 41, 47, 50, 52, and 57 (15 items)
- II. Lethargy (lethargy and social withdrawal): Items 3, 5, 12, 16, 20, 23, 26, 30, 32, 37, 40, 42, 43, 53, 55, and 58 (16 items)
- III. Stereotypic Behavior: Items 6, 11, 17, 27, 35, 45, and 49 (7 items)
- IV. Hyperactivity (hyperactivity and noncompliance): Items 1, 7, 13, 15, 18, 21, 24, 28, 31, 38, 39, 44, 48, 51, 54, and 56 (16 items)
- V. Inappropriate Speech: Items 9, 22, 33, and 46 (4 items)

The ABC will be administered at Baseline and at all post-baseline visits from (Week 2 through Week 52). Items are rated on a 4-point Likert scale ranging from 0 (not at all a problem) to 3 (the problem is severe), with higher scores indicating more severe problems. Subscale scores are calculated by summing the items within that subscale.

Missing ABC item scores will not be imputed. If any item is missing within a subscale, then that particular subscale score will be missing.

5.2.2 CGI-S

The CGI-S is a clinician-rated, 7-point scale that is designed to rate the severity of the subject's illness, in this study irritability associated with ASD, at the time of assessment, making use of the clinician's judgment and past experience with subjects who have the same disorder ([Guy 1976](#)). The CGI-S of irritability will be administered Baseline and at all post-baseline visits from (Week 2 through Week 52). The possible scores are 1=normal, not at all ill, 2=minimally ill, 3=mildly ill, 4=moderately ill, 5=markedly ill, 6=severely ill, 7=among the most extremely ill.

Missing CGI-S of irritability scores will not be imputed.

5.2.3 CGI-I

The CGI-I is a clinician-rated, 7-point scale that is designed to assess how much the subject's illness, in this study irritability associated with ASD, has improved or worsened relative to a baseline state at the beginning of the intervention ([Guy 1976](#)). The CGI-I of irritability will be administered at Baseline and at all post-baseline visits from (Week 2 through Week 52). The

possible scores are 1=very much improved, 2=much improved, 3=minimally improved, 4=no change, 5=minimally worse, 6=much worse, 7=very much worse.

Missing CGI-I of irritability scores will not be imputed.

5.2.4 Repetitive Behavior Scale-Revised (RBS-R)

The RBS-R ([Lam and Aman 2007](#)) is a 43-item parent/caregiver-facing questionnaire. Items are conceptually grouped into six subscales:

- stereotyped behavior (movements with no obvious purpose that are repeated in a similar manner): 6 items
- self-injurious behavior (actions that cause or have the potential to cause redness, bruising, or other injury to the body): 8 items
- compulsive behavior (behavior that is repeated and performed according to a rule or involves things being done “just so”): 8 items
- ritualistic behavior (performing activities of daily living in a similar manner): 6 items
- sameness behavior (resistance to change, insisting that things stay the same): 11 items
- restricted behavior (limited range of focus, interest, or activity): 4 items

Items are rated on a 4-point Likert scale ranging from (0) “behavior does not occur” to (3) “behavior occurs and is a severe problem”, and raters are asked to refer to the previous month when completing the scale. The total RBS-R score is calculated as the sum of all subscale scores.

Missing RBS-R item scores will not be imputed.

The RBS-R will be administered at Baseline, and at the Week 12, Week 28, Week 36, Week 44, and Week 52 visits.

5.2.5 Vineland Adaptive Behavior Scales–Socialization (VABS-Socialization)

The VABS is a parent/caregiver-facing measure of adaptive behavior, organized into three domains: communication, daily living skills, and socialization ([Sparrow et al. 2016](#)). Only the socialization domain will be used in this study.

The socialization domain is a 112 item questionnaire with 3 subdomains: interpersonal relationships, play and leisure and coping skills. Items are rated in a 0, 1, 2 scale. 2 (behavior is usually performed), 1 (behavior is sometimes performed), 0 (behavior is never performed).

Missing VABS-Socialization item scores will not be imputed.

The VABS–Socialization will be administered at Baseline, and at the Week 12, Week 28, Week 36, Week 44, and Week 52 visits.

5.2.6 Caregiver Strain Questionnaire

The Caregiver Strain Questionnaire (CGSQ) ([Brannan et al. 1997](#)) is a 21-item parent/caregiver-facing questionnaire of self-reported strain experienced since last visit by parents/caregivers and families of children and adolescents with serious emotional and behavioral disorders. Responses are on a 5-point Likert scale ranging from (1) “not at all a problem” to (5) “very much a problem”.

The following areas of caregiver strain are included:

- disruption of family life and relationships
- demands on time
- negative mental and physical health effects for any member
- financial strain
- sacrifice
- disruption of social/community life
- worry and guilt
- fatigue and strain
- embarrassment
- child-caregiver relationship

The total score is sum of the following three subscale scores:

- objective strain (mean of items 1-11),
- subjective internalized strain (mean of items 12, 16-18, 20-21), and
- subjective externalized strain (mean of items 13, 14 reversed, 15, 19).

Missing CGSQ item scores will not be imputed.

The CGSQ will be administered at Baseline, and at the Week 6, Week 20, Week 28, Week 36, Week 44, and Week 52 visits.

5.2.7 Columbia-Suicide Severity Rating Scale (C-SSRS)

The C-SSRS will be administered at Baseline and at all visits from Week 1 through Week 52, and at unscheduled visits. The C-SSRS monitors changes in suicidal thinking and behavior over time,

in order to determine risk ([Posner et al. 2011](#)). Four constructs are measured: the severity of ideation, the intensity of ideation, behavior, and lethality.

There are 5 questions about suicidal ideation, representing 5 types of suicidal ideation: wish to be dead; non-specific active suicidal thoughts; active suicidal ideation with any methods (not plan) without intent to act; active suicidal ideation with some intent to act, without specific plan; active suicidal ideation with specific plan and intent. If a subject/caregiver answers “yes” to any of these 5 questions, this subject will be counted as having suicidal ideation.

There are 5 questions about suicidal behavior, representing 5 types of suicidal behavior: preparatory acts or behavior; aborted attempt; interrupted attempt; actual attempt; suicide. If a subject answers “yes” to any of these 5 questions, this subject/caregiver will be counted as having suicidal behavior.

Missing C-SSRS item scores will not be imputed.

5.2.8 Tanner Staging

Tanner staging is a scale of physical development in children, adolescents, and adults. The scale defines physical measurements of development based on external primary and secondary sex characteristics, such as the size of the breasts, genitals, testicular volume, and development of pubic hair.

Tanner staging will be reported (by either the subject or the subject’s caregiver) at Baseline, Week 12, Week 28, Week 44, and Week 52 visits. The Tanner stages are defined as follows in [Table 1](#).

Table 1 Tanner Staging Classification

Sexual Characteristic	Tanner Stage	Female	Male
Breast development (female) or stage of genitalia (male)	Stage 1	Elevation of papilla only	Testes <2.5 cm
	Stage 2	Breast bud under the areola	Testes 2.5 to 3.2 cm
	Stage 3	Breast tissue grows but has no contour or separation	Testes 3.3 to 4.0 cm
	Stage 4	Projection of areola and papilla	Testes 4.1 to 4.5 cm
	Stage 5	Adult-type contour	Testes >4.5 cm

		Female/Male
Pubic hair development	Stage 1	Villus hair only
	Stage 2	Sparse hair
	Stage 3	Coarse hair
	Stage 4	Adult coarse hair, curly
	Stage 5	Adult hair, spreads to medial thigh

5.2.9 Extrapyramidal Symptom Rating Scale—Abbreviated (ESRS-A)

The ESRS ([Chouinard and Margolese 2005](#)) was developed to assess drug induced movement disorders such as parkinsonism, akathisia, dystonia, and tardive dyskinesia with established reliability, validity, and sensitivity. It consists of a questionnaire of parkinsonian symptoms, physician examination of parkinsonism, dyskinetic movements, and global impression of tardive dyskinesia. The ESRS-A, an accepted modified form of the original ESRS, will be used during the study to monitor for any worsening in extrapyramidal symptoms or signs at scheduled and unscheduled visits.

ESRS-A consists of 4 subscales and 4 clinical global impression movement severity scales of Parkinsonism, dyskinesia, dystonia, and akathisia. The Parkinsonism subscale consists of 10 items, the dyskinesia subscale consists of 6 items, the dystonia subscale consists of 6 items, and the akathisia subscale consists of 2 items. Each item is scored on a 6-point scale (0=absent, 1=minimal, 2=mild, 3=moderate, 4=severe, 5=extreme). The ESRS-A total score is the sum of the 24 item scores with a possible range of 0 to 120. Higher scores denote more severe symptoms of a movement disorder.

Missing ESRS-A item scores of the 4 subscales will not be imputed. The ESRS-A total score will be missing if any item score of the 4 subscales is missing.

Each clinical global impression movement severity scale of Parkinsonism, dyskinesia, dystonia, and akathisia is a single-item 6-point scale (0=absent, 1=minimal, 2=mild, 3=moderate, 4=severe, 5=extreme). The score ranges from 0 to 5, with higher scores indicating more severe movement disorders. Missing clinical global impression movement severity score will not be imputed.

The ESRS-A will be administered at Baseline and at all post-Baseline visits (Week 1 through Week 52), and at unscheduled visits.

5.3 Analysis Visits

5.3.1 Study Day

Study Day 1 is defined as the first dose date of open-label study drug (pimavanserin). If the date of assessment occurs on or after the first dose date, then study day will be calculated as (date of assessment – date of first dose) + 1. If the date of assessment occurs prior to the first dose date, then study day will be calculated as (date of assessment – date of first dose).

5.3.2 Analysis Visit Windows

The Baseline value is defined as the most recent non-missing value collected prior to the administration of the first dose of open-label study drug.

Efficacy and safety assessments will be summarized by analysis visits as presented in [Table 2](#) below.

Table 2 Analysis Visit Windows

Open-label (OL) Analysis Visit Name	Target Study Day ¹	Study Day Interval
OL Baseline	1	≤ 1
OL Week 2	15	2 to 28
OL Week 6	43	29 to 63
OL Week 12	85	64 to 112
OL Week 20	141	113 to 168
OL Week 28	197	169 to 224
OL Week 36	253	225 to 280
OL Week 44	309	281 to 336
OL Week 52	365	≥ 337

¹ If the assessment date \geq first OL dose date, study day = assessment date - first OL dose date + 1, otherwise study day = assessment date – first OL dose. Study day 1 is the first OL dose date.

5.3.3 Unscheduled Assessments

Both scheduled and unscheduled assessments, including early termination visits, will be considered for planned timepoint analyses based on the above analysis visit windowing rules. All assessments will be presented in data listings.

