### 6.4.1 Physical Examination and Self- or Caregiver-reported Tanner Staging

A general physical examination will be conducted.

Height will be measured and reported.

Weight will be measured and reported.

Body mass index will be calculated using the following formula:

$Weight (kg) / [height (m)]^2$ .

Tanner staging is a scale of physical development in children, adolescents, and adults. The scale defines physical measurements of development based on external primary and secondary sex characteristics, such as the size of the breasts, genitals, testicular volume and development of pubic hair ([Marshall and Tanner 1969](#); [Marshall and Tanner 1970](#)).

A physical examination will be administered, and Tanner staging will be reported (either by the subject or the subject's caregiver), at Baseline, and at the Week 12, Week 28, Week 44, and Week 52 visits.

Height (as measured by a stadiometer), weight, and BMI will be measured at Baseline, at all visits from Week 2 through Week 52, and at unscheduled visits.

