14.2 Clinical Laboratory Variables

Clinical laboratory tests are performed at Baseline, Week 2, Week 6, Week 12, week 20, Week 28, Week 36, Week 44 and Week 52 visits.

Due to COVID-19 disruptions it is possible that some test results may be collected from a local laboratory. Local laboratory results and the associated normal ranges will be converted to SI units; the local laboratory results, in SI units, will then be normalized to central lab ranges to be included in summary data analysis together with the central laboratory results. The normalization will be performed using the following scale transformation equation:

$$s = L_s + (x - L_x) \frac{U_s - L_s}{U_x - L_x}$$

where s is the normalized individual laboratory value to be used for summary; x is the original value from the local lab; L_x and U_x are the lower and upper limits from the local lab; L_s and U_s are the lower and upper limits from the central lab.

For labs with only a single upper (or lower) limit, the following scale transformation equation will be used:

$$s = x \frac{U_s}{U_x}$$

where s is the normalized individual laboratory value to be used for summary; x is the original value from the local lab; U_s is the upper (or lower) limit from the central lab; U_x is the upper (or lower) limit from the local laboratory. Local laboratory results and normalized results will be included in data listings. Only central lab and normalized local lab results will be used for summary of change from baseline, shift, and potentially clinically important (PCI) analyses.

Clinical laboratory tests include the following:

- Clinical chemistry serum tests
 - Sodium (Na), potassium (K), carbon dioxide (CO₂), chloride (Cl), phosphorus (P), calcium (Ca), blood urea nitrogen (BUN), creatinine (CR), glucose, albumin (ALB), total protein

- Alanine aminotransferase (ALT), aspartate aminotransferase (AST), gamma-glutamyl transpeptidase (GGT), alkaline phosphatase (ALP), total bilirubin (TBIL), lactate dehydrogenase (LDH)
- Lipid panel
 - Total cholesterol, high-density lipoprotein (HDL)-cholesterol, triglycerides, low-density lipoprotein (LDL)-cholesterol, cholesterol/HDL ratio, non-HDL cholesterol
- HbA_{1c}
- Prolactin
 - Prolactin results should be blinded to the Investigator and the Sponsor at Baseline. Results will be monitored by an independent Medical Monitor from the Clinical Research Organization (CRO).
- Creatine kinase (CK)/creatine phosphokinase (CPK)
- Pregnancy test

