14.2.1 Analysis of Clinical Laboratory Variables

14.2.1.1 Observed Values and Change from Baseline

All laboratory test results will be provided in the listings. The listings will include date and study day of collection. All units will be displayed in Système International [SI] units. Out of range values will be flagged in the data listings (e.g. 'L' or 'H').

Clinical laboratory values for hematology, chemistry and urinalysis will be summarized using descriptive statistics at Baseline, Week 3 and Week 6. The change from Baseline values will also be summarized at Week 3 and Week 6. The overall minimum and maximum post-baseline observed and change from Baseline values will also be summarized. For hemoglobin, hematocrit and uric acid, the above summaries will be presented for each gender as well as for both genders combined. For urinalysis with categorical results (blood, protein, glucose, and ketones), the number and percentage of subjects will be tabulated by category at Baseline, Week 3 and Week 6, with the denominator being the number of subjects with non-missing values for the given parameter, visit and cohort.

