14.2.1.3 Potentially Clinically Important (PCI) Laboratory Values

The number and percentage of subjects with PCI laboratory values at scheduled post-Baseline visits and overall post-Baseline (for the open-label treatment period) will be summarized by Baseline status (all and within normal range) for selected parameters. PCI criteria are listed in [Table 3](#) and [Table 4](#). For the overall post-baseline summaries of PCI values, all post-baseline values will be considered, including unscheduled and out of window values. Subjects with multiple PCI values for a given parameter will be counted only once for that parameter. For the by-visit summary, the numerator for the percentage is the number of subjects with a post-baseline PCI value for the given parameter, visit and cohort, and the denominator is the number of subjects with non-missing values for the given parameter, visit and cohort. For the overall post-baseline summary, the numerator for the percentage is the number of subjects with at least one post-baseline PCI laboratory value for the given parameter and cohort, and the denominator is the number of subjects with at least one post-baseline laboratory value for the given parameter and cohort. For hemoglobin, hematocrit and uric acid, the count and percentage of subjects with PCI values will be presented for each gender as well as for both genders combined. A listing of all PCI values in study -070 will be provided. This listing will include all observations from study -070 for those subjects and parameters for which at least one PCI value (including Baseline) was observed.

Table 3 Criteria for Potentially Clinically Important Laboratory Values – Hematology and Chemistry

Analyte	Conventional Unit	Low PCI Criteria	High PCI Criteria	SI Unit	Low PCI Criteria	High PCI Criteria
Hematology (whole blood)						
Hemoglobin (male)	g/dL	<11	>17	g/L	<110	>170
Hemoglobin (female)	g/dL	<10	>17	g/L	<100	>170
Hematocrit	%	<30	>50	L/L	<0.3	>0.50
Leukocyte (White Blood Cell Count)	x 10 ³ /uL	≤2.8	≥15	x 10 ⁹ /L	≤2.8	≥15
Neutrophils	x 10 ³ /uL	≤1.5	No upper limit	x 10 ⁹ /L	≤1.5	No upper limit
Eosinophils	%	No lower limit	≥10	L/L	No lower limit	≥10
Platelet Count	x 10 ³ /uL	≤75	≥700	10 ⁹ /L	≤75	≥700
Chemistry (serum or plasma)						
ALT (SGPT)	U/L	No lower limit	≥3 X ULN	U/L	No lower limit	≥3 X ULN
AST (SGOT)	U/L	No lower limit	≥3 X ULN	U/L	No lower limit	≥3 X ULN
Total Bilirubin	mg/dL	No lower limit	≥1.5 ULN	umol/L	No lower limit	≥1.5 ULN

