14.5.1 Physical Examination

Physical examination results (normal, abnormal, and not done) at Baseline, Week 12, Week 28, Week 44, and Week 52 will be summarized in a frequency table by cohort, body system and visit.

A listing of physical examination data will be provided.

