14.5.2 Tanner Staging

The Tanner staging at Baseline, Week 12, Week 28, Week 44, and Week 52 will be summarized in a frequency table by gender, category (Breast development [female] or Genitalia [male], and Pubic Hair Development) and visit.

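### Early-termination physical exams and Tanner stages falling in about half of the study days before the Week 52 window enter no summary table

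*SAP*

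**What the plan says.** SAP 5.3.2 applies a single window table to everything: "Efficacy and safety assessments will be summarized by analysis visits as presented in" Table 2. That table has windows for Weeks 2, 6, 12, 20, 28, 36, 44 and 52. SAP 5.3.3 then brings ET visits into the by-visit analyses: "Both scheduled and unscheduled assessments, including early termination visits, will be considered for planned timepoint analyses based on the above analysis visit windowing rules". SAP 5.3.4 keeps one result per window, the one closest to the target day.

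Protocol 6.4.1 schedules the physical exam and Tanner staging "at Baseline, and at the Week 12, Week 28, Week 44, and Week 52 visits". The SAP tabulates them at the same weeks. Section 14.5.1 reads: "Physical examination results (normal, abnormal, and not done) at Baseline, Week 12, Week 28, Week 44, and Week 52 will be summarized". Section 14.5.2 reads: "The Tanner staging at Baseline, Week 12, Week 28, Week 44, and Week 52 will be summarized in a frequency table by gender". Neither section asks for an overall post-baseline, worst-case or last-value summary. SAP 5.3.3 sends all assessments to listings, and 14.5.1 names a listing for the physical exam.

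For laboratory tests the documents disagree. The schedule of events and Protocol Table 6-1 place chemistry, hematology and urinalysis at Baseline, Weeks 12, 28 and 44, and Week 52/ET. SAP 14.2 says "Clinical laboratory tests are performed at Baseline, Week 2, Week 6, Week 12, week 20" and continues through every later visit. SAP 14.2.1.1 says that the values "will be summarized using descriptive statistics at Baseline, Week 3 and Week 6".

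**The concern.** The windows follow the full visit grid, but the exam and Tanner tables have rows for only four of the eight post-baseline visits. A child who stops on Day 150 has an ET exam in the Week 20 window, and these tables have no Week 20 row. The result is assigned to a timepoint and then not shown, which defeats the stated aim of SAP 5.3.3.

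The results affected are the last ones obtained from subjects who stopped. Without them, the by-visit exam tables describe mainly those who stayed on drug. Protocol 2.1.1 names physical examination among the safety evaluations. The analysis is descriptive throughout, so what a table leaves out is not recovered by any model or test.

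**Working it through.** **1. Reproduce Table 2.** The target days are 15, 43, 85, 141, 197, 253, 309 and 365. Each lower bound after the first is the midpoint of two neighbouring targets:

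- (15+43)/2 = 29
- (43+85)/2 = 64
- (85+141)/2 = 113
- (141+197)/2 = 169
- (197+253)/2 = 225
- (253+309)/2 = 281
- (309+365)/2 = 337

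All seven match the SAP. The windows were built on all eight visits, not on the schedule of any one assessment.

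**2. Windows with no exam or Tanner row.**

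| Window | Days | Length |
|---|---|---|
| Week 2 | 2-28 | 27 |
| Week 6 | 29-63 | 35 |
| Week 20 | 113-168 | 56 |
| Week 36 | 225-280 | 56 |
| Total | | 174 |

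The days before the Week 52 window are Days 2-336, that is 335 days. 174/335 = 51.9%. Counting every possible ET day up to Day 364 gives 174/363 = 47.9%.

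**3. Subjects affected.** The documents give N of about 193 (Protocol 9.3, SAP 3.5) but no dropout rate or timing for the extension. The rates and timing patterns below are assumptions. Each count is 193 × dropout rate × share of ET visits in a gap window. It assumes that every dropout attends an ET visit with an exam.

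| Dropout | Stop early | Uniform, Days 2-336 (51.9%) | Uniform, Days 2-364 (47.9%) | Constant hazard (49-52%) | Front-loaded Weibull, shape 0.6 (60-63%) |
|---|---|---|---|---|---|
| 20% | 39 | 20 | 19 | 19 | 23 |
| 30% | 58 | 30 | 28 | 29 | 35 |
| 40% | 77 | 40 | 37 | 39 | 47 |
| 50% | 96 | 50 | 46 | 50 | 61 |

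**4. Second loss, from the closest-to-target rule.** Suppose scheduled exams take place exactly on Days 85, 197 and 309. An ET result on Days 86-112, 198-224 or 310-336 then shares a window with a scheduled exam at distance zero and is not selected. That is 27+27+27 = 81 further days, or 81/335 = 24.2%. The subject still appears in that row, but with the earlier result.

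**5. Would assessment-specific windows solve it?** Applying the same midpoint rule to Weeks 12, 28, 44 and 52 gives (85+197)/2 = 141, (197+309)/2 = 253 and (309+365)/2 = 337. The windows become Days 2-140, 141-252, 253-336 and 337 onward, and the unassigned days fall from 174 to 0. The closest-to-target rule would still discard ET results on Days 86-140, 198-252 and 310-336: 55+55+27 = 137 days, or 137/335 = 40.9%. A Day 10 result would also be labelled Week 12.

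**6. Laboratory tests, read three ways.**

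- On the schedule of events, ET labs in the gap windows have no by-visit row.
- On SAP 14.2, a Day 150 ET lab has a Week 20 row, but that row holds only ET and unscheduled draws.
- On SAP 14.2.1.1, Table 2 has no Week 3 window, the Week 6 row holds only ET and unscheduled draws, and the scheduled labs from Week 12 onward are not tabulated by visit.

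On any reading, the overall minimum and maximum (14.2.1.1), the shifts to them (14.2.1.2) and the overall potentially clinically important counts (14.2.1.3) keep ET values, as SAP 5.3.4 directs.

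**The case against.** The strongest reply is that little safety information is lost. Adverse events are counted from first dose to 30 days after last dose, with no visit windows. Events leading to discontinuation have their own summary and listing. Under Protocol 7.1.1 an adverse event includes any unfavorable sign, so a new adverse finding at an ET exam should be reported as one. The exam results are also listed. All of this stands, and it is why the point is minor. It does not restore a rate: a listing does not show how many dropouts had an abnormal exam, and the tables that would show it omit them. For Tanner staging, a reported developmental stage, the link to tolerability is weaker still.

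A reader might infer that ET laboratory results are lost in the same way. The documents do not support that. The SAP contradicts itself on lab timepoints, so no fixed share of by-visit losses can be stated, and the overall summaries keep lab extremes on every reading.

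A reader might also extend the point to the RBS-R, VABS-Socialization and CGSQ, which skip some visits. SAP 13.1 tabulates only the endpoints listed in 12.1, and none of the three is there, so no by-visit table is specified from which values could drop. CGSQ is an exploratory endpoint in Protocol 2.3.1 and 9.5.4. Its absence from SAP 12.1 is a separate matter and not a windowing fault.

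**Conclusion.** The point holds for physical examination and Tanner staging. ET results on 174 of the 335 days before the Week 52 window (52%) enter no summary table, although SAP 5.3.3 says that ET visits count towards the timepoint analyses. Further ET results lose to a scheduled visit nearer the target day. The share of days follows from the SAP alone. The number of subjects does not: about 20 to 50 rests on assumed dropout of 20% to 50% of 193, uniform timing over those 335 days and an ET visit for every dropout. Earlier dropout would raise it.

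Severity is minor. It would be wrong to conclude that the primary safety result is biased towards those who tolerate the drug: the primary endpoint is untouched, and the documents do not say how often subjects stop because of an adverse event. For laboratory tests the conclusion is conditional, since the conflict between SAP 14.2, SAP 14.2.1.1 and the schedule must be settled before the by-visit loss can be defined.

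**What to change.** Add to the tables in SAP 14.5.1 and 14.5.2 an end-of-treatment row giving each subject's last non-missing post-baseline result. For the physical exam, add a row for any abnormal post-baseline result by body system. Both rows should use all post-baseline results, including ET and unscheduled ones.

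Assessment-specific windows are optional. They remove the gaps but, as step 5 shows, are not sufficient alone.

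For laboratory tests, first reconcile SAP 14.2 and 14.2.1.1 with the schedule of events and Protocol Table 6-1. Then add the same end-of-treatment row to the by-visit change tables.

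The cost is SAP text and a little programming, with no new data and no protocol change. The drawback is one or two extra rows per table that mix different times on treatment. A footnote giving the median and range of study day for the end-of-treatment row would make that visible.
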